variable selection, where the most important predictors are chosen from a set of predictors to build a parsimonious model (21). Another machine learning technique is Principal Component Analysis (PCA), which finds groups of correlated predictors amongst a large set of potential predictors (i.e. dimensionality reduction) (21). The most important groups of predictors could then be placed in a model. Other modeling techniques we will use include classification trees, which predict outcomes based on input variables through classification, random forest to show which predictor has the highest importance, and association rule learning to help profiles of linked predictors (21).

Foundational papers on machine learning of intraoperative data have reported inconsistent results. Prasad et al. analyzed data from 101 patients undergoing liver transplantation and showed that intraoperative hemodynamic data improved the prediction of mortality and acute renal failure compared to preoperative information alone (22). On the contrary, Lee et al. found that a deep neural network model predicted in-hospital mortality, though not better than conventional models such as the Risk Stratification Index (23). It is important for clinicians to understand the factors and processes by which the machine learning algorithm built the model, to help with clinical decision making and hypothesis generation for future research. Thus, we have chosen machine learning techniques that generate interpretable models. Our use of a large population database and advanced machine learning methods may help improve our understanding of the crucial relationships amongst hemodynamic variables and complex perioperative data.

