At the time of surgery, anesthesiologists document the timing of key clinic information (induction, intubation, start and end of surgery, emergence, extubation, and exit of the operating room), medications and fluids administered, estimated blood loss, and type of anesthesia into the intraoperative record. Hemodynamic factors are automatically recorded into the database every minute. The following intraoperative hemodynamic factors will be included in model building:

Table 1. Exposures

Blood pressure	
Since there is no universal definition of low blood pressure under anesthesia, we will use several different variables to determine the most significant exposure by threshold and duration. Both Systolic Blood Pressure (SBP) and Mean arterial pressure (MAP) have been used in blood pressure research (12). In a recent study (26), different blood pressure modeling techniques on the same dataset led to different conclusions on the impact of hypotension on postoperative myocardial infarction and kidney injury. Methods with the largest odds ratios were absolute maximum decrease in MAP and mean episode area under threshold. However, since the area under threshold is less interpretable and difficult to calculate in everyday clinical practice, the duration under threshold will be used.
 
SBP
 
1. Maximum change from preoperative SBP, in a) absolute change (mmHg), and b) relative change (%) (emergency and elective cases analyzed separately due to the lack of preoperative blood pressure in the emergency group)2. Cumulative duration (minutes) $\geq 20\%$ below preoperative SBP3. Longest single episode (minutes) below a) 80, b) 90, and c) 100 mmHg4. Cumulative duration (minutes) below a) 80, b) 90, and c) 100 mmHg 
MAP
 
1. Maximum change from preoperative MAP, in a) absolute change (mmHg), and b) relative change (%) (emergency and elective cases analyzed separately due to the lack of preoperative blood pressure in the emergency group. Note that since the HSM database only contains SBP and DBP, not MAP, MAP will be calculated using $MAP = 1/3*SBP + 2/3*DBP$)2. Cumulative duration (minutes) $\geq 20\%$ below preoperative MAP3. Longest single episode (minutes) below a) 60, b) 65, c) 70, and d) 80mmHg4. Cumulative duration (minutes) below a) 60, b) 65, c) 70, and d) 80mmHg
-----------------------	---

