 5. Delirium
 6. Septic Shock
2. Postoperative ICU admission (yes/no)
3. Prolonged Postoperative Length of Stay (LOS) (greater than vs. less than or equal to CIHI Expected Length of Stay (ELOS) as assigned by the Case Mix Grouping) [note that the LOS includes the day of surgery]
4. Hospital readmission within 30 days (yes/no)
5. Intraoperative mortality (yes/no)
6. Days alive and out of hospital at 30 days postoperatively (28)

III. Other predictors included into model

The following potential perioperative predictors will be evaluated as covariates during model building. Statistically significant predictors will be retained in the model.

Table 2. Other predictors

Preoperative	
 1. Demographics: age on date of surgery, sex, obesity (body mass index>30) 2. Indicators of preoperative comorbidities: since no comorbidity score has perfect performance, a variety of models will be evaluated and the most significant predictive score will be retained in the model. 
 • American Society of Anesthesiologist class • RCRI score(29), and specific components via ICD codes (history of ischemic heart disease, congestive heart failure, cerebrovascular disease, diabetes, chronic kidney disease, and CCI and Case Mix Group codes of suprainguinal vascular, intraperitoneal, or intrathoracic surgery) using previously published methods (30)(31) • Elixhauser comorbidity index (32) and Charlson Comorbidity Index (33): calculated using diagnoses from the previous three years according to standard algorithm by HDNS. Reported as both total score and individual categories • Hospital Frailty Risk Score (34): based on ICD codes • Preoperative blood pressure: ICD diagnosis of hypertension and by measured blood pressure • Preoperative heart rate: Innovian and HSM • Chronic Obstructive Lung Disease (ICD code): since it may affect the interpretation of results of SpO₂ and EtCO₂ 3. Indicators of surgical complexity 
 • CIHI DAD Case Mix Group (CMG) class (also contains categories that include medical complexity) • Main Surgical Service • Procedural Index for Mortality Risk (PIMR) (35): according to CCI • Procedure: CCI codes • Preoperative ICU admission • Emergency surgery: as determined by DAD Method of Entry = emergency department or transferred from another institution)

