- The following blood pressure artifact removal rules as described by Salmasi et al (41) will also be applied: “SBP less than or equal to DBP + 5 mmHg”, and “abrupt changes defined by SBP change greater than or equal to 80 mmHg within 1 min in either direction or abrupt SBP changes greater than or equal to 40 mmHg within 2 min in both directions.”

3. To remove artifacts prior to arterial line insertion, for IABP data only, the first MAP readings must be >40 , and the first SBP reading must be >60 .
4. For each BP measurement, if any of SBP or MAP has been labelled as an artifact, then remove the entire measurement.
5. If an entire case has been identified as null after artifact removal (i.e. no valid BP for the entire case), the entire case and studyID will be deleted.

2. Step 2. Concatenation. The final blood pressure will be taken from IABP or NIBP, whichever is available after artifact removal. If both non-invasive (NIBP) and invasive blood pressure values (IABP) are available for the same 15 second interval, the higher reading will be taken. Otherwise, the only blood pressure that is valid will be used.

3. Clarification re. “Baseline” blood pressure: The HSM and first Innovian BP will be modeled separately during analysis, i.e. each patient will have two “baseline” measurements, coded by the variables “MAP_first_Innovian” and “MAP_preop_HSM”.

1. All patients will have the variable of a first Innovian BP (after artifact clean up). The first Innovian BP is used since the second BP may be postinduction. This has the limitation that the the first intraoperative BP may not reflect the true baseline (42); however, practically this would be the blood pressure that would be available in similar clinical situations.
2. Only some patients will have HSM BP (i.e. at preoperative clinic or in the preadmission area). Since the HSM does not contain MAP, MAP will be calculated using $MAP = (2/3 DBP) + (1/3 SBP)$.
 - If a patient does not have a HSM BP, the variable value will be coded as missing (not zero).

- **Heart rate**

1. Artifact removal:
 1. The heart rate will be collected from the pulse oximeter instead of ECG, to reduce risk of electric cautery artifact and non-transmitted conduction.

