Since intraoperative hemodynamics are automatically recorded and mortality reporting is mandatory, we do not expect significant missing data for the key hemodynamic predictors and primary outcomes. For disease conditions, patients without ICD codes are assumed to not have the disease; the same applies for medications. For the other variables of interest, if there is less than 5% missing data, no processing will be performed. Between 5-20%, missing data will be imputed using group mean (43) for continuous variables. At greater than 20% missing data, the variable will be removed from analysis with potential causes evaluated and reported.

Creating the models

We will divide the cohort temporally (approximately 80:20 ratio) into two groups: derivation/training group (approx. January 1, 2013 – Dec 31, 2016), and validation group (approx. Jan 1, 2017 – December 1, 2017). This temporal approach to the model building vs. validation groups will also mirror the real-life application of machine learning, where data from the past is used to predict future outcomes. Splines will be used for the hemodynamic predictors involving time as a unit.

In the derivation/training set, we will create models for the *primary outcome* using machine learning techniques, including logistic regression with variable selection, classification trees, and Principal Component Analysis (PCA)(21). We have chosen these techniques to obtain interpretable results, i.e. being able to understand the process by which the algorithm decision making occurred. Also, these techniques demonstrate different approaches and perspectives to better understand the relationships amongst the variables.

Logistic regression with variable selection (e.g. LASSO, Elastic Net) identifies the most important predictors to create a parsimonious model. Classification trees predict outcomes based on input variables through classification. Random forest is an ensemble method of classification trees; while it is not directly interpretable, it can show which predictor has the highest importance. Association rule learning will be used to find new patterns. PCA is used for

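### Random-forest importance ranked variable by variable can place a weaker single predictor above a stronger vital sign that is split over many overlapping definitions

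*Combined protocol and SAP*

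**What the plan says.** Under Creating the models, the combined protocol and SAP says of the random forest that "while it is not directly interpretable, it can show which predictor has the highest importance". Background and significance gives the same purpose: "random forest to show which predictor has the highest importance". Neither place says whether importance is impurity-based or permutation-based, whether definitions of the same vital sign are grouped, or how uncertainty is shown.

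Table 1 is introduced with "The following intraoperative hemodynamic factors will be included in model building". For blood pressure it explains that "we will use several different variables to determine the most significant exposure by threshold and duration". The entries include "Longest single episode (minutes) below a) 80, b) 90, and c) 100 mmHg" for systolic pressure and "Cumulative duration (minutes) below a) 60, b) 65, c) 70, and d) 80mmHg" for mean arterial pressure (MAP). Under Data processing and artifact removal, the plan adds that "The HSM and first Innovian BP will be modeled separately during analysis", which can multiply the baseline-dependent variables. Table 2 supplies the competing covariates: "The following potential perioperative predictors will be evaluated as covariates during model building". Some of these enter once, such as age and sex. Others describe the same thing several times, such as ASA class, RCRI, Charlson, Elixhauser and frailty.

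**The concern.** A forest shares credit among predictors that can stand in for one another. If one vital sign is offered in 20 overlapping versions, each version is chosen for only some of the splits. Shuffling one version also costs little, because the others still carry the information. The rank of a single variable then depends partly on how many versions of it were listed, and not only on how strongly the underlying sign relates to death.

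The lay summary gives the objective as finding which vital signs, and at what levels, may be harmful. A list headed by a covariate entered once could be read as evidence that hypotension matters less than that covariate, when the order comes from how the variables were laid out. The best-performing model is also to be used for the secondary outcomes, so if the forest were chosen, its ranking could be carried further.

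**Working it through.** **1. The plan's own figure.** Power calculation gives 24,000 × 0.017 = 408 deaths in the derivation group, and 408 / 10 = 40.8, rounded to 41 predictors. This reproduces. The documents give no figure for variable importance.

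**2. Count of Table 1 variables.**
- Systolic pressure: 2 (maximum change, absolute and relative) + 1 (minutes at least 20% below baseline) + 3 + 3 (thresholds) = 9.
- MAP: 2 + 1 + 4 + 4 = 11.
- Blood pressure in all: 9 + 11 = 20. If the 6 baseline-dependent variables are built for both baselines, 20 + 6 = 26.
- Heart rate 7 to 9 (depending on whether positive and negative changes count separately), SpO2 4, EtCO2 4, medications 5. Total 40 to 42 before the second baseline.

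**3. Overlap by construction.** A minute below MAP 60 is also a minute below 65, 70 and 80. The longest episode below a threshold cannot exceed the cumulative minutes below it.

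**4. Simulations.** Both use logit P(death) = a + b1 × BP + b2 × covariate, with a set to give 1.7% deaths and b1 > b2. Permutation importance of a variable or block is the held-out AUC minus the held-out AUC after shuffling that variable or block. Effects, correlations and forest settings are assumptions; the documents give none.

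*Simulation A.* 24,000 derivation and 7,000 validation patients, 50 predictors, 20 blood-pressure variables with mutual correlation 0.7, 60 trees, 24 runs. Odds ratio per SD: 1.6 for blood pressure, 1.4 for one covariate.
- Weaker covariate ranked first by impurity: 92% of runs.
- Weaker covariate ranked first by held-out permutation: 38%. Monte Carlo standard error: √(0.375 × 0.625 / 24) = 0.10.
- All 20 blood-pressure variables permuted together: blood pressure above the covariate in 96%.

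*Simulation B.* 24,000 training and 6,000 held-out patients, 20 replicates, 100 trees. The 20 definitions were computed from simulated minute-level pressures (mean absolute correlation about 0.57, median about 0.68). One independent covariate and 10 noise variables were added. Log-odds per SD: 0.8 for blood pressure, 0.5 for the covariate.

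| True effect acts through | BP variables in forest | Impurity: best BP / covariate | Covariate ahead of every BP variable, impurity | Same, permutation |
|---|---|---|---|---|
| Minutes below MAP 65 (log scale) | 1 | 0.241 / 0.140 | 0/20 | 0/20 |
| Minutes below MAP 65 (log scale) | 20 | 0.058 / 0.089 | 20/20 | 19/20 |
| Underlying MAP level | 1 | 0.195 / 0.148 | 2/20 | 0/20 |
| Underlying MAP level | 20 | 0.060 / 0.092 | 20/20 | 18/20 |

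Within each pair of rows only the number of blood-pressure definitions changes, so that number causes the reversal.

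**5. Grouped permutation in simulation B, all 20 definitions.** Mean AUC loss was 0.187 for the blood-pressure block against 0.038 for the covariate, and 0.165 against 0.041 in the second scenario. Blood pressure was ahead in 20/20 both times. The best single definition had shown losses of only 0.012 and 0.015.

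**6. Adding up impurity scores does not repair it.** With no true effect at all, the 20 blood-pressure columns still summed to 0.47 of total impurity importance.

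**7. Accuracy.** Mean held-out AUC with 1 against 20 definitions was 0.730 against 0.730, and 0.709 against 0.716.

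**The case against.** The strongest reply is that nothing in the plan is decided by the forest ranking. That stands. A reader might infer that the forest selects the predictors, but the text only describes what a forest can show. Covariate retention in Table 2's introduction rests on statistical significance, the primary hypothesis is an association adjusted for other predictors, and measures of association for the thresholds are planned separately.

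Entry of all 20 definitions into one forest is also inferred. With one definition per sign the splitting largely disappears (0/20 to 2/20 above). This stands as a condition on the point.

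The plan does handle correlated predictors through PCA and a sensitivity analysis of definitions. But the second PCA feeds a logistic regression, and the sensitivity analysis is not tied to the forest ranking. Neither repairs that ranking.

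A reader might infer that covariates always gain at the expense of vital signs. The documents do not support this. Comorbidity appears as several scores plus their categories and is diluted too. Surgery duration and BIS minutes overlap with the minute-count exposures, since longer cases allow more minutes past any threshold. The net direction in the real data is unknown.

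The rates are not firm. If the 0.7 correlation in simulation A reflects one common factor carrying the effect, each definition's own odds ratio is about exp(0.47 × √0.7) = exp(0.47 × 0.84) = 1.48, close to the rival's 1.4. This does not apply to simulation B's MAP 65 scenario, where one listed definition carries the whole effect and is still outranked.

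Finally, a reader might object that a ranking names a winner even when nothing predicts death. That is true of any ranking, and the planned validation would expose it: with no effect, held-out AUC in simulation B averaged 0.496.

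**Conclusion.** The point holds in a limited form. If the overlapping Table 1 definitions enter one forest, a per-variable importance ranking can put a weaker predictor entered once above a truly stronger vital sign. In the simulations the weaker covariate was ahead in 38% to 95% of runs by permutation and 92% to 100% by impurity. The spread reflects the assumed effects, correlations and forest settings, so the figures show that the reversal can be common but do not predict its rate in this cohort. The same dilution affects any covariate block with several overlapping members. Discrimination was almost unchanged, so the planned performance measures would not reveal the problem. Because the forest is descriptive and one of several methods, this is a change the plan should make, not a threat to its primary analysis.

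**What to change.** State in Creating the models that forest importance will be reported as grouped permutation importance on the validation set. All definitions of one vital sign (blood pressure, heart rate, SpO2, EtCO2, medications) are permuted together, and likewise each overlapping covariate block such as comorbidity, with intervals. Rank individual definitions only within a vital sign, as a secondary display. Say also whether all Table 1 definitions enter the same forest. Summed impurity scores should not be used in place of joint permutation.

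Intervals matter because the validation set has few deaths. If 24,000 is 80% of the cohort, the remaining 24,000 / 0.8 − 24,000 = 6,000 patients give 6,000 × 0.017 = 102 deaths. If validation is 20% of 35,000, 7,000 × 0.017 = 119. A reference distribution from refitting on permuted mortality is an optional addition.

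The cost is one or two sentences and modest computing, with no new data. The downside is that single-definition ranks become secondary.

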Several techniques exist to make the learning algorithms to focus on the important class (44). Among these, pre-processing techniques are a powerful tool enabling the use of any standard learning algorithm by modifying the training set. The goal is to obtain a more balanced training set through weighting, undersampling and/or oversampling. We will explore different resampling techniques to rebalance the training set. Regarding undersampling, we will explore both random and informed undersampling (remove examples near the decision border through nearest neighbours computation and use a clustering algorithm to guide the selection of examples). For oversampling, we will explore the introduction of replicas (randomly or by weighting) and the generation of synthetic data through the introduction of Gaussian Noise, SMOTE, and other SMOTE-based techniques. We will also examine the combination of these techniques. All of these techniques are only applied on the training set used to learn the model, and they are never applied on the test set. Thus, the model, although learned in a more balanced scenario is always evaluated only in real data and in a real imbalanced scenario.

We will also apply cost-sensitive learning. The assignment of higher costs to type II errors during learning has the potential to improve the results, reducing this type of error. The effect of class rebalancing (at a variety of ratios and through a variety of techniques) on model performance will be examined, and the impact of these adjustments on model performance will be reported.

Evaluating model performance

Using the derivation/testing set, the performances of machine learning models generated will be evaluated by cross validation. To account for potential temporal effects and concept drift, Monte Carlo and prequential evaluation will be used (45). In addition, each model will be evaluated in terms of discrimination, calibration, and risk reclassification (21,46). Discrimination will be calculated through C-statistics using area under curve (AUC) of receiver operating characteristic curve (ROC). Calibration will be represented graphically using observed vs.

expected event rates in risk estimate deciles, and by the Hosmer-Lemeshow statistic. Brier score will be computed for discrimination and calibration. Risk reclassification will be quantified through Yates slope and integrated discrimination improvement. R-squared will be reported.

The performance of all models created will be evaluated in the validation set as part of internal validation using the same metrics of discrimination, calibration, and risk reclassification, and compared to the Surgical Apgar Score. Since there will likely be significant class imbalance and ROC curves may overestimate model performance, for each model, precision and recall curves (PRC), F score, average precision, and AUC will also be reported and compared. The best performing model will also be used to analyze for predictors for secondary outcomes. Sensitivity (recall, true positive rate), specificity, positive predictive value (precision), G-mean, negative predictive values, False Discovery Rates (FDR), optimism, and measures of association of hemodynamic thresholds for primary and secondary outcomes will be computed. Bayesian network causal inference analysis may be performed, to help increase interpretability.

Sensitivity and subgroup analysis

Sensitivity analysis will be performed for different definitions of hemodynamic derangements. Subgroup analysis will be performed based on age, sex, high preoperative risk (most significant indicator of preoperative comorbidity in Table 2, based on final model), RCRI, frailty (HFRS), preoperative hypertension, a select list of intermediate-high risk, gender-neutral elective surgery (please see Appendix – RCRI Protocol Table 1), emergency surgery, and type of anesthesia.

Power calculation

The 2016-2017 in-hospital mortality after major surgery in Nova Scotia is 1.7% (47). Using the Events Per Variable criterion (EPV) of at least 10 outcomes per predictor in the sample, the 1.7% mortality (408) out of an estimated sample size of 24,000 for the derivation/training group means that our model would be valid for up to 41 predictors for the primary outcome. However, the EPV may over or underestimate the limitations of the EPV criterion (48), square root of the mean squared prediction error (rMPSE) and mean absolute prediction error (MAPE) will be calculated based on the number of predictors, sample size and events fraction (49) with the caveat that this model has not been externally validated. Full power calculation will be performed once we receive the final sample size.

Strengths

This study involves a large, recent population dataset with nearly complete follow up for the primary outcome. There has been more than 10 years of experience with intraoperative anesthetic electronic recording system, with a high likelihood of provider proficiency with anesthetic intraoperative electronic documentation. This dataset is unique in North America for its degree of intraoperative details, pairing of clinical and administrative data, and robust data quality. Our use of machine learning could detect new network relationships and strategies that may inform current practice as well as future research.

Limitations

This study involves two academic provincial adult non-obstetric tertiary care centres in one hospital system, which may represent a sicker population. Validation in other centres would

increase generalizability. The retrospective nature of this database study makes it susceptible to random error, bias, and confounding. There may be cluster effects from health providers and hospitals, however the large sample size allows for robust power and minimizes random error. There is a potential for misclassification, measurement, and ascertainment bias. Due to the lack of universal screening for morbidity (e.g. troponin biomarker for myocardial injury and infarction, and Brain-Natriuretic Peptide for preoperative cardiac risk stratification), only mortality will be included as primary outcome. The lack of postoperative hemodynamic data creates non-informative censoring (i.e. unbiased since the data is missing for all patients). Numerous other predictors have been adjusted for through multivariate logistic regression but unknown confounders and confounding by indication may remain. The retrospective data reflects a snapshot of evolving practice, though secular effects may remain limited over the five-year study period. Future prospective validation of the prediction model will increase external validity.

Future directions

Future research includes prospective multicentre validation of our findings. Based on this model, a real-time risk prediction tool could be incorporated into electronic anesthesia management systems, while a simple score could be developed for clinicians. In addition, randomized studies could shed light on whether targeted hemodynamics, increased postoperative follow-up based on risk stratification, and real-time machine learning precision medicine could improve mortality, morbidity, and patient-reported outcomes after surgeries.

Feasibility

Budget overview

Budget Item	Amount	Details
A. Personnel/third party service providers	\$800	Mentorship from data analyst [name].
B. Equipment	\$0	SAS and R software will be provided by HDNS.
C. Materials, supplies and administrative services	\$5895 \$75	Health Data Nova Scotia data request and linkage with Innovian and HSM. Medavie patient ID encryption (required by HDNS)
D. Knowledge translation and dissemination	\$1600	Poster presentation at a conference
Total	\$8370	

Additional budget details

Budget Item A: [name] is a data analyst within the Department of Surgery with extensive experience with HDNS. She has been contracted to mentor [name] data analysis for 16 hours at \$50/hour (\$800).

Budget Item C: We will request Discharge Abstracts Database and Vital Statistics data from Health Data Nova Scotia (HDNS) (please see confirmation of feasibility and quote attached). HDNS will link this dataset with our institutional Innovian (intraoperative anesthesia electronic record) by MSI and provide us with a complete de-identified dataset. No server purchase is necessary since the HDNS data will be provided on Citadel. Details from HDNS regarding Citadel: "Analyses will be carried out remotely on the HDNS Windows server "Citadel". Connection to Citadel occurs through Remote Desktop Connection (RDC). Citadel only accepts connections from approved DAL NetIDs to access specific project data housed in our Hadoop based research cluster. Other external connections such as the internet or USB devices are disabled, and no data may be transferred between the local PC and the remote session."

Budget Item D: Presentation at a conference: Poster printing \$200, flights and accommodation \$1000, registration fee \$400.

Funding: \$5000 Nova Scotia Health Authority Research Fund (awarded), the rest to be covered by the Dalhousie Department of Anesthesia

Benefits

This interdisciplinary study brings together investigators from diverse disciplines and locations, with expertise from Dalhousie anesthesiology, epidemiology, and Big Data Institute, as well as Harvard and University of Toronto. The research project is locally-based and relevant, with findings that may spark further research and inform anesthesiology perioperative practice.

The QEII hospitals are tertiary referral centres taking care of some of the sickest patients of the province. Better understanding of intraoperative predictors may unveil strategies to improve outcome and improve resource allocation after surgery. Moreover, this model may be generalizable to other hospitals, placing the Nova Scotia Health Authority and Dalhousie University as a leading innovator in this area, as large population-level outcomes research will likely continue to be at the forefront of health research.

Research team roles and responsibilities

[name] is completing the Harvard T.H. Chan School of Public Health Summer-Only Master of Science in Epidemiology. This consists of coursework over three summers (2018-2020) and online. The courses focus on epidemiology and advanced statistics, and with mentorship from Harvard and Dalhousie faculty [name] has been learning the theoretical knowledge and practical coding skills to independently analyze this project. She has protected research time to complete this project.

